9.2 Dose-Limiting Toxicity

The following definitions of dose-limiting toxicity (DLT) apply to both the safety lead-in (Section 9.3) and the continuous toxicity monitoring rule (Section 9.4). DLTs are defined as the following toxicities which are attributed to the study drug(s) and not to disease, and which occur (or first become evident) during a prespecified timeframe. For the purposes of the safety lead-in, this timeframe is the first two cycles of treatment. For the purposes of the continuous toxicity monitoring rule, this timeframe is the first four cycles of treatment.

1. Any grade ≥ 3 non-hematologic toxicity, except grade ≥ 3 fatigue, nausea, or vomiting which must persist > 5 days despite maximal supportive care to be considered dose limiting.
2. Any grade ≥ 4 hematologic toxicity lasting > 14 days, except grade 4 lymphopenia, which is not considered a DLT.
3. Grade ≥ 3 neutropenia with fever
4. Grade ≥ 3 thrombocytopenia with clinically significant bleeding
5. Any laboratory abnormality not otherwise addressed above which is associated with clinical sequelae and which fails to resolve to grade ≤ 1 within 5 days of occurrence, or any laboratory criteria meeting Hey's law for liver toxicity.
6. Any event leading to dose reduction or permanent discontinuation of any study drug during cycles 1-2 (applies to safety lead-in subjects only).

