In a phase 1 study in patients with advanced solid tumors, the maximum tolerated dose (MTD) of belinostat was 1000 mg/m² IV daily, administered over 30 minutes on Days 1-5 of a 21-day cycle (Steele *et al.*, 2008). Dose-limiting toxicities (DLTs) included grade 3 fatigue, diarrhea, and atrial fibrillation, as well as grade 2 nausea/vomiting resulting in inability to complete a full 5-day cycle. A phase 1 study in patients with advanced hematologic neoplasms reported the same MTD (Gimsing *et al.*, 2008). The most common treatment-related adverse events (AEs) (all grades) were nausea (50%), vomiting (31%), fatigue (31%), and flushing (31%). There was one case of grade 3 lymphopenia and two cases of grade 4 renal failure in the context of tumor lysis syndrome (TLS). The only related grade 3 events in more than one patient were fatigue and neurologic symptoms, and no cardiac events were noted. Oral belinostat was studied in 15 patients who were included in the phase 1 trial of IV belinostat in second or subsequent treatment cycles (Steele *et al.*, 2011). High doses, up to 1000 mg/m² orally twice daily for 5 consecutive days, were found tolerable in this small study. In a phase 1 trial of oral belinostat in patients with lymphoma, the drug was found to be safe (no DLTs) at daily doses of 750-1250 mg on Days 1-14 every 3 weeks (Zain *et al.*, 2009). In a phase 2 clinical trial, belinostat was administered IV at 1000 mg/m² daily on Days 1-5 every 21 days in patients with relapsed/refractory AML or newly diagnosed patients with AML over the age of 60 (Kirschbaum *et al.*, 2015). Belinostat was well tolerated; however, only 4 patients displayed stable disease (SD) for at least five cycles. A similar trial of belinostat at the same dose and schedule showed similar activity in myelodysplastic syndrome (MDS), with only one confirmed response (Cashen *et al.*, 2012).

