6.2.3 Belinostat

6.2.3.1 Concomitant medications and supportive guidelines

Belinostat is associated with nausea. **Patients must receive prophylactic treatment with a 5-HT3 receptor antagonist for the first two cycles of treatment.** Ondansetron (oral disintegrating tablet 8 mg PO or equivalent) may be administered once prior to each dose of belinostat. Alternatively, granisetron extended-release injection 10 mg SC may be administered once on day one prior to the first administration of belinostat in each treatment cycle. If nausea or vomiting occurs despite the use of a 5-HT3 receptor antagonist, consider the addition of dexamethasone 8-10 mg PO or IV prior to each dose of belinostat. Continuation of the 5-HT3 receptor antagonist after the first two cycles is at the treating investigator's discretion.

As discussed in Section 6.2.1.1 and 6.2.2.1, patients will be administered prophylactic growth factor.

Patients should receive all supportive care appropriate for their medical condition, including, but not limited to, antibiotics, transfusions, and other agents deemed necessary for symptom management, unless specifically prohibited elsewhere in the protocol.

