7.4 Dose Modifications for Hematologic Toxicity

Both study agents are associated with myelosuppression. In order to begin a new treatment cycle, criteria specified in Section 7.3 must be met. A delay of up to 4 weeks is permitted to allow toxicity to resolve and initiate a new cycle of treatment. If counts have not recovered despite a 4 week delay from the scheduled start date, the patient should be discontinued from the study. Because the agents are administered concurrently, it may be difficult to attribute hematologic toxicity to one of the two agents with certainty. In general, SGI-110 (guadecitabine) or ASTX727 (whichever agent the patient is receiving) is associated with more frequent myelosuppression than belinostat. Therefore, a stepwise approach to dose modification is recommended, beginning with SGI-110 (guadecitabine) or ASTX727, as shown in the table below. If the investigator believes a hematologic toxicity is clearly attributable to one of the two drugs, that drug may be preferentially modified.

Observed Hematologic Toxicity (at any time during cycle)	Recommended Management
ANC <500/ μ L Hemoglobin <7 g/dL Platelets <25,000/ μ L	Delay cycle. Monitor complete blood count at least weekly. Transfuse and/or use growth factor per institutional guidelines. When criteria for a new cycle are met, resume at one dose level lower , per the table immediately below.
Grade 3 or 4 neutropenic fever	
Grade 3 thrombocytopenia with bleeding	

Other hematologic AEs deemed clinically significant and for which dose modification is deemed necessary by the treating investigator.	
ANC 500-999/ μ L Hemoglobin 7.0-7.9 g/dL Platelets 25,000-74,999/ μ L	
Delay cycle. Monitor complete blood count at least weekly. Transfuse and/or use growth factor per institutional guidelines. When criteria for a new cycle are met, resume at the same dose if the delay was 14 days or less, otherwise resume at one dose level lower, per the table immediately below.
 
If hematologic toxicity requiring a dose reduction occurs, and a delay is also needed, only one dose reduction is applied.

Hematologic Toxicity Event	Recommended Management
First Event	Reduce SGI-110 (guadecitabine) or ASTX727 by one dose level
Second Event	Reduce belinostat by one dose level
Third Event	Reduce SGI-110 (guadecitabine) or ASTX727 by one dose level
Fourth Event	Reduce belinostat by one dose level

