7.5 Dose Modifications for Non-Hematologic Toxicity

Toxicity Grade	Management of Agent Causing Toxicity
Diarrhea	
Grade 1	Continue treatment. Evaluate for infectious etiology if clinically indicated. Institute anti-diarrheal therapy with loperamide.
Grade 2	Continue treatment. Evaluate for infectious etiology if clinically indicated. Institute anti-diarrheal therapy with loperamide. If grade 2 diarrhea persists for more than 3 days despite supportive care, interrupt treatment or delay cycle and manage supportively until symptoms improve to grade ≤ 1 . At next cycle, reinitiate treatment at same dose. For recurrent grade 2 diarrhea lasting more than 3 days despite supportive care, manage as above, but resume treatment when resolved to grade ≤ 1 at one dose level lower for the agent to which toxicity is attributed.
Grade 3	Interrupt treatment or delay cycle until symptoms improve to grade ≤ 1 . Evaluate for infectious etiology if clinically indicated.
Grade 4	Institute anti-diarrheal therapy. At next cycle, resume treatment at one dose level lower for the agent to which toxicity is attributed.
Fatigue	
Grade 1	Continue treatment. Evaluate for other causes of fatigue including infection or anemia.
Grade 2	Continue treatment. Evaluate for other causes of fatigue including

	infection or anemia. If grade 2 fatigue persists for more than 3 days and is deemed intolerable by the patient or treating investigator, interrupt treatment or delay cycle until resolved to grade ≤ 1 . At next cycle, reinitiate treatment at same dose.
Grade 3	Interrupt treatment or delay cycle until grade ≤ 1 . At next cycle, resume treatment at one dose level lower for the agent to which toxicity is attributed.
Vomiting	
Grade 1	Continue treatment. Escalate supportive care. Consider addition of dexamethasone prior to treatment.
Grade 2	Continue treatment. Escalate supportive care. Consider addition of dexamethasone and/or additional anti-emetics prior to treatment, per NCCN Guidelines for Supportive Care. If grade 2 vomiting persists for more than 3 days, interrupt treatment or delay cycle until resolved to grade ≤ 1 . At next cycle, reinitiate treatment at same dose.

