Grade 3	Interrupt treatment or delay cycle until improved to grade ≤ 1 . Escalate supportive care. Consider addition of dexamethasone and/or additional anti-emetics prior to treatment, per NCCN Guidelines for Supportive Care. At next cycle, resume treatment at one dose level lower for the agent to which toxicity is attributed.
Grade 4	Discontinue offending agent.
Other Non-Hematologic Toxicity	
Other grade 3 AEs deemed clinically significant by the treating investigator*	Interrupt treatment or delay cycle until event resolves to grade ≤ 1 or baseline. Resume at one dose level lower for the study agent to which toxicity is attributed.
Grade 4 (except alopecia, clinically insignificant laboratory abnormalities or AEs described elsewhere in this section)	Discontinue offending agent.

*Treatment may also be interrupted for grade 2 non-hematologic toxicities deemed intolerable by the patient, until such toxicity is resolved to grade 1 or baseline. If intolerable toxicities persist >4 weeks despite supportive care, the agent responsible for the toxicity should be discontinued.

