9.3 Safety Lead-In

Recognizing that SGI-110 (guadecitabine) and belinostat have not been formally evaluated together, but that previously completed studies have shown DNA hypomethylating agents and

HDAC inhibitors are generally well tolerated in combination, we will perform a safety lead-in among six patients to confirm safety and tolerability of the proposed dose and schedule.

The safety lead-in will apply to the first six patients treated for two cycles (8 weeks). These patients will undergo safety assessments as specified in the study calendar. The study will not proceed to further accrual until these six patients have completed two cycles or 8 weeks of study treatment; however, patients who end study treatment during this period for reasons other than toxicity, *i.e.*, disease progression, will not be replaced. At that time, the study investigators, CTEP, and the DSMB (if applicable) will review the safety data. If two or more patients in the safety lead-in population experience DLTs as defined in Section 9.2, the study team, CTEP, and the DSMB (if applicable) will consider terminating the study, amending the study to evaluate a lower dose level, and/or further evaluating safety at the current dose level among a limited number of additional patients, and the amended protocol and rationale for modification will be submitted to the CIRB for review. The study team, CTEP, and the DSMB (if applicable) may also take such action if safety concerns exist even in the absence of 2 or more DLTs occurring during the safety lead-in. Formal documentation of the study team's review of toxicity data from the safety lead-in will be provided prior to resuming accrual.

With Amendment 5, the study was modified to substitute AST727 for SGI-110 (guadecitabine). The safety lead-in period will be repeated as described among the first 6 patients treated with ASTX727 and belinostat. However, the safety lead-in period for belinostat and ASTX727 will use a DLT monitoring period of 4 weeks (instead of 8 weeks). The continuous toxicity monitoring rule discussed below will continue to monitor for later-onset toxicity. Definitions of DLT remain the same.

Investigators are expected to report any DLT events directly to the study statistician and the Data Coordinating Center within 24 hours of their knowledge of such an event.

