9.4 Continuous Toxicity Monitoring Rule

In addition to the safety lead-in, a continuous toxicity monitoring rule will be applied to this study to monitor for excessive or unexpected toxicity associated with study treatment (Ivanova *et al.*, 2005). Patients will be subjected to continuous toxicity monitoring during the first four cycles of study treatment. Sequential boundaries will be used to monitor the DLT rate. DLTs are defined in Section 9.2 above. According to this model, shown in the table below, enrollment will be halted if the number of DLTs is equal to or exceeds b_n out of n patients with completed DLT follow-up. This is a Pocock-type stopping boundary which yields a probability of crossing the boundary (early stopping) of at most 30% stopping when the rate of DLT is equal to the acceptable rate of 20% using a pre-defined sample size of 26 patients. This boundary is equivalent to testing the null hypothesis, after each patient, that the event rate is equal to 0.20, using a one-sided level 0.14 test.

With Amendment 5, the study was modified to substitute ASTX727 for SGI-110 (guadecitabine). The continuous toxicity monitoring rule will apply as defined above to patients treated with belinostat and ASTX727. Toxicities experienced by the initial cohort of 6 patients treated with SGI-110 (guadecitabine) and belinostat will not be considered in the model as it

applies to subsequent patients treated with ASTX727 and belinostat.

If the early stopping event occurs, the study will be halted and the investigators, CTEP, and the DSMB (if applicable) will discuss whether to close the study early for toxicity or modify the protocol to address the observed events. In addition, if any grade 5 event at least possibly related to study treatment occurs, the study will also be halted for review in this fashion.

Number of patients (n)	1	2	3	4	5	6	7	8	9	10	11	12	13
Boundary, b_n	-	2	2	3	3	3	4	4	4	4	5	5	5
Number of patients (n)	14	15	16	17	18	19	20	21	22	23	24	25	26
Boundary, b_n	5	6	6	6	6	7	7	7	7	8	8	8	8

Investigators are expected to report any DLT events directly to the study statistician and the Data Coordinating Center within 24 hours of their knowledge of such an event.

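### The vomiting exemption in the DLT definition has no upper grade, so grade 4 vomiting of 5 days or less that ends an agent is not itself counted by the toxicity rule after the lead-in

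*Combined protocol and SAP*

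**What the plan says.** Section 9.2 gives one list of DLTs for both the safety lead-in (9.3) and the continuous monitoring rule (9.4).

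- **Item 1** counts every grade ≥3 non-hematologic toxicity attributed to study drug. The exception, also written at grade ≥3, is for "fatigue, nausea, or vomiting which must persist" beyond 5 days under maximal supportive care. No upper grade is given.
- **Items 2-4** are hematologic. **Item 5** concerns laboratory abnormalities with clinical sequelae that do not resolve, and liver criteria.
- **Item 6** counts any dose reduction or permanent discontinuation, but only for lead-in subjects and only in cycles 1-2. Section 9.3 shortens the ASTX727 lead-in window to 4 weeks.

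Section 9.4 applies these definitions over the first four cycles and halts enrollment when the DLT count reaches the tabulated boundary. It adds one trigger outside the count: review "if any grade 5 event at least possibly related to study treatment occurs".

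In Section 7.5 the instruction for grade 4 vomiting is "Discontinue offending agent", with no duration condition. For grade 4 diarrhea it is "Institute anti-diarrheal therapy. At next cycle, resume treatment at one dose level lower".

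**The concern.** After the lead-in, 9.4 is the only numerical stopping rule for toxicity, and Section 9 says the combination has had no phase 1 dose-finding study. A patient could have drug-attributed grade 4 vomiting, lose an agent under 7.5, and add nothing to the count. A patient with grade 4 diarrhea, who resumes one dose level lower, adds one. Nothing in the documents explains why the allowance for short-lived nausea and vomiting should reach grade 4.

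The 9.4 window covers cycles 1-4, but antiemetic prophylaxis is mandatory only in cycles 1-2. Section 6.2.3.1 then says: "Continuation of the 5-HT3 receptor antagonist after the first two cycles is at the treating" investigator's discretion. Part of the window therefore lies outside mandatory prophylaxis.

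What is at stake is whether one kind of grade 4 event enters the safety count.

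**Working it through.** **1. Trace of the event.** Take drug-attributed grade 4 vomiting lasting 5 days or less in patient 7 or later.

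| Provision | Does it count the event? |
|---|---|
| 9.2 item 1 | No: exempt at grade ≥3 unless longer than 5 days |
| 9.2 items 2-4 | No: hematologic |
| 9.2 item 5 | Not the vomiting itself; only a qualifying laboratory abnormality |
| 9.2 item 6 | No: lead-in subjects, cycles 1-2 |
| 9.4 separate trigger | No: grade 5 only |

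A separate grade ≥3 non-hematologic consequence would count under item 1. For patients 1-6 the gap opens when item 6 stops applying: after cycle 2 by its own text, or after 4 weeks if the 9.3 window governs. Because related grade 5 events halt the study anyway, the gap is grade 4 only. Grade 4 diarrhea meets item 1 on onset.

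**2. The plan's own figure.** The 9.4 boundaries for n = 1 to 26 are: none, 2, 2, 3, 3, 3, 4, 4, 4, 4, 5, 5, 5, 5, 6, 6, 6, 6, 7, 7, 7, 7, 8, 8, 8, 8. Each is the smallest r with P(X ≥ r | n, 0.20) ≤ 0.14, and all printed values match. Let f(n,k) be the probability of k DLTs after n patients without having halted. Then f(n,k) = f(n-1,k)(1-p) + f(n-1,k-1)p, and any mass with k ≥ b_n is removed as a halt. At p = 0.20 the total halting probability is 0.293, consistent with the stated ceiling of 30%.

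**3. Effect of counting the event.** The documents give no rate for it. Assume a proportion v of patients has such an event and no other DLT, with patients independent and the rate constant. In the 20% column other DLTs stay at 20% and p becomes 0.20 + v. In the 30% column the total rate including these events is 30%, so the rule as written sees 0.30 - v.

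| v | P(at least one in patients 7-26) = 1-(1-v)^20 | Halting, 20% other DLTs: as written → edited | Halting, 30% total: as written → edited |
|---|---|---|---|
| 0.1% | 2.0% | 0.293 → 0.297 | 0.682 → 0.685 |
| 0.5% | 9.5% | 0.293 → 0.312 | 0.667 → 0.685 |
| 1% | 18.2% | 0.293 → 0.331 | 0.649 → 0.685 |
| 2% | 33.2% | 0.293 → 0.370 | 0.611 → 0.685 |

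The added halting at 30% (about 0.35, 1.8, 3.6 and 7.4 points) is matched almost one for one by the added halting from a 20% base (0.4, 1.9, 3.8 and 7.7 points).

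If item 6 already captures these events in patients 1-6, the differences shrink. For v = 0.5%, 1% and 2%, the 20% column becomes 0.301 → 0.312, 0.310 → 0.331 and 0.327 → 0.370. The as-written values at 30% become 0.674, 0.663 and 0.640.

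**4. How one event can matter.** The boundary at n = 13 is 5. Suppose four other DLTs have accrued without an earlier crossing and patient 13 has short grade 4 vomiting. The edited definition gives 5 and halts enrollment; the current one leaves 4 and enrollment continues. This shows the mechanism; it is not a likely path.

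**The case against.** The strongest reply is that the plan keeps DLT status and loss of an agent apart, so the asymmetry is not a contradiction. That stands:

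- Section 7.1 lets patients with a DLT continue after dose modification, and item 6, the only clause that counts discontinuation, is deliberately limited to the lead-in.
- Section 7.5 also ends an agent for intolerable toxicity beyond 4 weeks, including grade 2, which does not meet item 1.
- A reader might infer from Section 7.4 ("When criteria for a new cycle are met, resume at one dose level lower") that short hematologic events never end an agent, which would single vomiting out. Sections 7.1 and 7.4 do not support this: treatment stops if counts have not recovered after a 4-week delay, so a grade 4 cytopenia too short for item 2 can still end treatment.

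Two other tempting supports fail. The belinostat phase 1 DLTs in 2.2.1.2 included "grade 2 nausea/vomiting resulting in inability to complete a full 5-day cycle", but the proposed edit would not count a grade 2 event either. A picture of grade 4 vomiting continuing through all five dosing days conflicts with 7.5, which stops the offending agent.

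The event is also likely to be rare. Section 6.1 reports no DLTs and mainly grade 1/2 vomiting for azacitidine with belinostat at the same belinostat dose. Life-threatening vomiting would still be reported to NCI within 24 hours under 10.3.3, although that report does not enter the 9.4 count.

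What survives is narrower: among grade 4 non-hematologic toxicities, only those in the item 1 exemption can go uncounted on grounds of duration.

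**Conclusion.** The point holds as a cheap improvement. On the text, drug-attributed grade 4 vomiting of 5 days or less is not itself a DLT in 9.4 for patients 7-26, or for patients 1-6 once item 6 lapses, unless a separate grade ≥3 consequence or item 5 qualifies. That conclusion needs no assumption.

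Its size does. At an assumed 0.1% to 2% of patients, the halting probability from a 20% base moves from 0.293 to between 0.297 and 0.370, and the true rate could lie outside that range. The effect is probably very small.

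A reader might conclude that the plan means every agent-ending toxicity to count, or that the edit makes the rule better at telling acceptable from excessive toxicity. Neither is supported: other agent-ending routes go uncounted, and the gain at 30% is offset by extra halting at 20%. The benefit is only that grade 4 vomiting is counted like other non-exempt grade 4 non-hematologic events.

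**What to change.** In 9.2 item 1, change the grade attached to the fatigue, nausea and vomiting exception from ≥3 to 3. Keep the more-than-5-days condition for grade 3, the scope of item 6 and the 9.4 boundary table. Grade 4 vomiting attributed to study drug then counts in 9.3 and 9.4 whatever its duration.

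The costs are:

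- One symbol in the text, but a protocol amendment to make it.
- A recheck of grade 4 vomiting in any ASTX727 patients already treated, so that the count uses one definition.
- Slightly more halts. With 0.5, 1 or 2 points added to a 20% rate, mean enrollment falls from 21.1 to 20.8, 20.6 or 20.0 of 26. A halt leads to discussion, not automatic closure.
- Confirmation by the study team that 20% is still the acceptable DLT rate under the slightly wider definition.

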9.3 Safety Lead-In

Recognizing that SGI-110 (guadecitabine) and belinostat have not been formally evaluated together, but that previously completed studies have shown DNA hypomethylating agents and

HDAC inhibitors are generally well tolerated in combination, we will perform a safety lead-in among six patients to confirm safety and tolerability of the proposed dose and schedule.

The safety lead-in will apply to the first six patients treated for two cycles (8 weeks). These patients will undergo safety assessments as specified in the study calendar. The study will not proceed to further accrual until these six patients have completed two cycles or 8 weeks of study treatment; however, patients who end study treatment during this period for reasons other than toxicity, *i.e.*, disease progression, will not be replaced. At that time, the study investigators, CTEP, and the DSMB (if applicable) will review the safety data. If two or more patients in the safety lead-in population experience DLTs as defined in Section 9.2, the study team, CTEP, and the DSMB (if applicable) will consider terminating the study, amending the study to evaluate a lower dose level, and/or further evaluating safety at the current dose level among a limited number of additional patients, and the amended protocol and rationale for modification will be submitted to the CIRB for review. The study team, CTEP, and the DSMB (if applicable) may also take such action if safety concerns exist even in the absence of 2 or more DLTs occurring during the safety lead-in. Formal documentation of the study team's review of toxicity data from the safety lead-in will be provided prior to resuming accrual.

With Amendment 5, the study was modified to substitute AST727 for SGI-110 (guadecitabine). The safety lead-in period will be repeated as described among the first 6 patients treated with ASTX727 and belinostat. However, the safety lead-in period for belinostat and ASTX727 will use a DLT monitoring period of 4 weeks (instead of 8 weeks). The continuous toxicity monitoring rule discussed below will continue to monitor for later-onset toxicity. Definitions of DLT remain the same.

Investigators are expected to report any DLT events directly to the study statistician and the Data Coordinating Center within 24 hours of their knowledge of such an event.

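### The six-patient safety lead-in sets no minimum number of DLT-evaluable patients and does not replace early leavers, so its two-DLT trigger can run on fewer than six informative patients

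*Combined protocol and SAP*

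**What the plan says.** Section 9.3 states the plan: "we will perform a safety lead-in among six patients to confirm safety and tolerability of the proposed dose and schedule". Accrual waits until the six have been through two cycles or 8 weeks, with an exception for "patients who end study treatment during this period for reasons other than toxicity". The text glosses this group as "disease progression, will not be replaced".

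The trigger is a fixed count: "If two or more patients in the safety lead-in population experience DLTs as defined in Section 9.2", the study team, CTEP and any DSMB will consider terminating, amending to a lower dose level, or treating a limited number of further patients. They "may also take such action if safety concerns exist even in the absence of 2 or more DLTs" have occurred.

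Amendment 5 carries the scheme over: "The safety lead-in period will be repeated as described among the first 6 patients treated with ASTX727 and belinostat". The difference is that the new lead-in "will use a DLT monitoring period of 4 weeks (instead of 8 weeks"). Section 9.3 adds that the DLT definitions are unchanged, yet Section 9.2 reads "For the purposes of the safety lead-in, this timeframe is the first two cycles of treatment", and its item 6 also refers to cycles 1-2.

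No section defines DLT-evaluable for the lead-in. Sections 9.8.1 and 12.1.1 make a patient evaluable for toxicity from first treatment. Section 9.4 does otherwise: its boundary is applied to patients with completed DLT follow-up.

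**The concern.** A patient who leaves inside the window without a DLT, and is not followed to its end, still fills one of the six places and adds nothing to the count. The trigger does not adjust. Any resulting error runs one way, toward finding the regimen tolerable.

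This matters because Section 9 says that neither combination went through a phase 1 dose-finding study, and Section 6.1 says that ASTX727 has not been studied with an HDAC inhibitor. The lead-in review is the step that must be passed before accrual resumes. Because Section 9.3 uses i.e. and names only progression, it is also unclear how it treats a patient who withdraws or is non-compliant, both of which Section 6.3 lists as reasons for stopping.

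**Working it through.** **The plan's own figure.** The documents give no operating characteristic for the lead-in. The nearest is in Section 9.4: a crossing probability of at most 30% at a true DLT rate of 20% over 26 patients, from a one-sided 0.14-level test after each patient. Exact recursion over n = 1 to 26 with the printed boundary gives 29.3%, and every printed boundary value matches the 0.14 rule. That figure stands.

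**Lead-in inputs.** Six patients and a trigger of two with DLTs (Section 9.3). The true DLT rate p and the number of informative patients m are varied. With independent patients,

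P(2 or more DLTs) = 1 − (1−p)^m − m·p·(1−p)^(m−1).

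At p = 0.40:
- m = 6: 1 − 0.0467 − 0.1866 = 0.767
- m = 5: 1 − 0.0778 − 0.2592 = 0.663
- m = 4: 1 − 0.1296 − 0.3456 = 0.525

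| True DLT rate | m = 6 | m = 5 | m = 4 |
|---|---|---|---|
| 20% | 34.5% | 26.3% | 18.1% |
| 30% | 58.0% | 47.2% | 34.8% |
| 40% | 76.7% | 66.3% | 52.5% |
| 50% | 89.1% | 81.3% | 68.8% |

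At rates of 30-50%, one wholly uninformative patient costs about 8 to 11 points, and two cost about 20 to 24.

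**Partial information.** The table is a worst case, since a DLT before leaving still counts. Suppose that each leaver is observed for half the window with constant hazard. At p = 0.40 the leaver's DLT probability is 1 − √0.60 = 0.225. With one leaver:
- P(0 DLTs) = 0.0778 × 0.7746 = 0.0602
- P(1 DLT) = 0.2592 × 0.7746 + 0.0778 × 0.2254 = 0.2183
- P(2 or more) = 72.2%

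With two such leavers it is 67.0%.

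**Random loss.** The documents give no early drop-out rate, so let q be an assumed chance that a patient leaves with no DLT information. The trigger probability is the six-patient formula with p(1−q) in place of p.

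| Assumed q | P(2 or more DLTs), p = 0.40 | P(two or more of six lost) |
|---|---|---|
| 0 | 76.7% | 0% |
| 5% | 73.4% | 3% |
| 10% | 69.9% | 11% |
| 20% | 62.2% | 34% |

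**The continuous rule as a backstop.** At p = 0.40 its cumulative crossing probability is 51.8% by 6 completed patients, 74.6% by 13 and 92.7% by 26. It needs three DLTs at n = 4 to 6. Its window is four cycles, so at a 4-week review few or no patients would have completed follow-up.

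**The case against.** The strongest reply is that leavers in the ASTX727 cohort are seldom unobserved. Dosing is on Days 1-5, so a patient who stops later in cycle 1 has had that cycle's scheduled doses. The study calendar requires an off-study examination, blood count, chemistry and adverse-event review within 21 days of the last dose. Serious events are reportable for 30 days after it (Section 10.3.3). The first on-treatment imaging is at 8 weeks, so exits for progression seen on scheduled scans should be uncommon in a 4-week window. Section 9.2 item 6 also counts drug-attributed events that lead to dose reduction or discontinuation as lead-in DLTs.

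Most of this stands, and it limits the size. It does not remove the gap. After a last dose on Day 5, the off-study visit falls no later than Day 26 (5 + 21) and may be earlier. Serious-event reporting runs to Day 35 (5 + 30), but not every DLT in Section 9.2 is a serious event. Clinical progression and withdrawal can occur at any time.

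A reader might infer that the lead-in silently becomes two of four and loses much of its sensitivity. The documents do not support that. Two wholly uninformative losses are needed, no drop-out rate is given, and the review must be formally documented before accrual resumes.

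Nor is the lead-in the only formal check. Reviewers may act on fewer than two DLTs, any at least possibly related grade 5 event halts the study, and the continuous rule runs alongside. These are partial backstops: the first is discretionary, the second covers deaths only, and the third matures late. Finally, two DLTs oblige reviewers only to consider action, so the probabilities above are not stopping probabilities.

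**Conclusion.** The gap is real and modest. Section 9.3 keeps a fixed two-DLT trigger without replacing early leavers or setting a minimum evaluable number, a looser standard than Section 9.4 applies. At a true DLT rate of 40%, one patient with no DLT information lowers the chance of reaching the trigger by about 10 points, or about 5 if half the window was seen (76.7% to 72.2%). Only two wholly uninformative patients make the loss large, about 24 points.

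The working expectation of zero or one loss is an assumption based on the 4-week window and the 8-week imaging. The two-cycle window in Section 9.2 would leave more time for early exits, so the conflict between the sections bears on the size.

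**What to change.** In Section 9.3, define DLT-evaluable as having had a DLT, or having been followed for DLTs to the end of the lead-in window. For the lead-in decision only, replace any patient who is not DLT-evaluable with the next stage-1 patient. The original patient stays in the efficacy and safety analyses. Leavers who were followed to the end of the window need no replacement.

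Replacements come from the planned 26 ASTX727 patients, so the study total stays at 26 + 6 = 32. The expected number treated to obtain six evaluable patients is 6/(1−q): 6.3, 6.7 or 7.5 for assumed q of 5%, 10% or 20%. The cost is time. Each replacement extends the accrual hold by one patient's accrual time, roughly 2 to 4 weeks at the 1-2 per month in Section 9.5, plus the DLT window. Restoring six informative patients also restores the 34.5% chance of reaching the trigger at the acceptable 20% rate, against 26.3% with five.

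Reconcile the lead-in window between Section 9.2 (two cycles, and item 6) and Section 9.3 (4 weeks for ASTX727), because it decides who counts as an early leaver. The documents do not say whether the ASTX727 lead-in is complete. If it is, report the number DLT-evaluable beside the DLT count.
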